
Table 1: Phase I: Identification of Recommended Phase II Dose		
Dose Level	MTD exceeded	Day +21 pSTAT3+ CD4+ T-cells <35%
Dose cohort 1 (100 mg daily)	Yes (Stop, do not proceed)	Yes (treat a total of 6, RP2D identified if ≤1/6 have DLT)
	No (Proceed)	No (Proceed to cohort 2)
Dose cohort 2 (100 mg BID)	Yes (Stop, return to complete 6 subjects in cohort 1)	Yes (treat a total of 6, RP2D identified if ≤1/6 have DLT)
	No (Proceed)	No (Proceed to cohort 3)
Dose cohort 3 (200 mg BID)	Yes (Stop, return to complete 6 subjects in cohort 2)	
	No (RP2D identified, proceed to phase II component of trial))	

The definitions for DLTs on PAC/SIR/TAC are as follows (CTCAE v4):

- 1. Left ventricular systolic dysfunction grade 3 or above*
- 2. Myocardial infarction grade 3 or above
- 3. Atrial fibrillation or flutter grade 3 or above
- 4. Supraventricular tachycardia grade 3 or above
- 5. Ventricular arrhythmia grade 3 or above
- 6. Upper or lower gastrointestinal hemorrhage grade 3 or above
- 7. Intracranial hemorrhage grade 1 or above
- 8. Any grade 3 or above adverse event considered at least possibly related to pacritinib

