Contemporary clinical trials have observed rates of VOD ranging from 8-9%. 35,36 Severe VOD is associated with a mortality rate in excess of 90%. The management of VOD primarily consists of eliminating exposure to offending agents and supportive care. Early phase clinical trials investigating the use of defibrotide in VOD have reported complete response rates up to 60%. 7 Patients will be monitored closely for any clinical signs of VOD. The specific management of any occurrence of VOD will be at the discretion of the physician of record.

c. Non-infectious diarrhea

Diarrhea is a known side effect of allogeneic HCT. Additionally, phase I-III studies of pacritinib in hematologic malignancies shows that grade 1-2 diarrhea is a common side effect of this medication. The pacritinib diarrhea typically occurs within 7 days of initiating the medication. Clinical trial data supports that the diarrhea does respond to anti-motility agents, and does not typically require dose reduction of pacritinib. Given the potential for compounding toxicities early after allogeneic HCT, dose reduction rules for diarrhea (1500ml/day x3 consecutive days, not responding to anti-motility agents) are provided in Table 1 of this protocol.

d. QTc prolongation

Life-threatening and sometimes fatal cardiac events have been observed in patients treated with pacritinib, including heart failure and arrhythmias, some of which may have been associated with sudden death. As such, EKGs will be performed at baseline as part of vital organ testing (VOT) and repeated at day +30 and day +60. Patients with a baseline QTc >450ms at time of VOT will be excluded from participation. Instructions for QTc >450ms that develop while taking pacritinib are provided in appendix D.

e. Coagulation parameters (TT, PT, and PTT)

Serious bleeding events, specifically bleeding of the brain (intracranial hemorrhage, subdural hematoma, cerebral hemorrhage), have been observed in association with pacritinib treatment and occasionally with life-threatening or

fatal outcomes. TT, PT, and PTT will be performed at baseline as part of vital organ testing (VOT) and repeated at day +30 and day +60. Patients with baseline TT, PT, and/or PTT >2x the upper limit of normal are excluded from participation. Instructions for a TT, PT, and/or PTT lab value >2x the upper limit of normal while on pacritinib are provided in appendix D.

6. Endpoints

Primary Endpoints

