The PI of this study will have responsibility for continuous monitoring of adverse events on this trial. Additionally, these events will be reviewed formally in monthly research meetings of the BMT program. As described in appendix C of this protocol, there are numerous anticipated adverse consequences of transplantation, which include, but are not limited to conditioning regimen related toxicity such as severe mucositis, idiopathic pneumonia syndrome, hepatic veno-occlusive disease and death, early and late infectious complications, potentially severe or fatal acute or chronic graft vs. host disease, and relapse of primary disease and its complications. As these are anticipated complications, they will not inform specific stopping criteria for toxicity in this study. If four related grade 4-5 unexpected adverse events occur in the conduct of this trial, an analysis will be performed, and further accrual to the trial will be temporarily halted. Data

will be analyzed, and a report will be submitted to the protocol monitoring committee (PMC). Further decisions regarding resuming accrual will be determined by the PMC with input from the PI of this study. If the study requires suspension or termination, an NHLBI Program Official will be notified in writing.

Scientific Review Committee (SRC)

The Cancer Center's internal SRC provides the review for scientific merit and prioritization and monitors scientific progress for all protocols at the Cancer Center. The SRC has a defined membership representing all of the major research divisions of the cancer center, including biostatisticians. The SRC reviews newly proposed clinical research studies based on the following categories:

- a. study significance to evaluate its potential for contribution to medical science.
- b. the adequacy of study objectives, design, specific aims and hypotheses.
- c. the methods to be employed to conduct the study. Ensuring that the study is adequately described, including inclusion/exclusion criteria, sample size, procedures and instruments to be used.
- d. Feasibility of the study. Ensuring the investigator has adequate staffing and facilities to conduct the study. Ensuring that the timeframe for the study and projected annual accrual are adequately addressed.
- e. Review of all data and safety monitoring plans.

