This informed consent should be given by means of a standard written statement, written in non-technical language. The subject should read and consider the statement before signing and dating it, and should be given a copy of the signed document. If the subject cannot read or sign the documents, oral presentation may be made or signature given by the subject's legally appointed representative, if witnessed by a person not involved in the study, mentioning that the patient could not read or sign the documents. No patient can enter the study before his/her informed consent has been obtained. The informed consent form is considered to be part of the protocol, and must be submitted by the investigator with it for IRB/IEC/REB approval.

Reporting of changes or amendments to the protocol or consent form

All changes or amendments to the protocol or consent form will be reviewed by the SRC and/or IRB. Once the revised documents are approved, they will be distributed to the FDA, NHLBI, and CTI BioPharma.

3. Safety: Monitoring of adverse events and pacritinib dose modifications for toxicity

Dose Adjustments for Pacritinib

Version 8.0 24

Specific dose adjustment rules are provided here for diarrhea, QTc prolongation, and left ventricular dysfunction (see below sections and tables). For all other pacritinib-related (probably or definitely) \geq Grade 3 non-hematologic toxicity, the following rules apply:

- Discontinue pacritinib administration until toxicity resolves to Grade 2 or better
- Once toxicity has returned to grade 2 or better, patients can resume pacritinib at 100mg less per
 day than the previously administered dose at which they were discontinued. Only two, 100mg,
 dose reductions are allowed before treatment with pacritinib is discontinued. Patients cannot
 reduce the dose of pacritinib <100mg daily. Patients that do not tolerate 100mg pacritinib daily
 must discontinue pacritinib. Following dose reductions, pacritinib dose re-escalation is not
 permitted.
- Patients who do not recover (≤ Grade 2 or baseline) within 14 days of discontinuation of study drug will not be permitted to re-start study drug.

Pacritinib Dose Management Guidelines for QTcF Interval Prolongation and Left Ventricular Dysfunction

Dose management for QTcF interval prolongation is summarized below.

QTc prolongation: CTCAEv4 Toxicity Grade	Management/Action
G1 (QTcF > 450ms)	No change
G2 (first occurrence)	Hold treatment:

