(QTcF > 480ms)	- hold minimum of one day, e.g. two doses on
	the 100mg BID dose level
	- then repeat EKG and consider resuming
	dosing if toxicity resolves to ≤ grade 1-If the
	toxicity resolves to ≤ grade 1 within 7 days,
	treatment may be resumed at next lowest
	dose level
	Toxicity that does not resolve to ≤ grade 1
	within 7 days requires treatment
	discontinuation
G2 (second occurrence)	Discontinue treatment
G3 and G4	Discontinue treatment
(QTcF > 500ms)	

After dose reduction, no dose re-escalation is allowed.

All patients are required to have an ECG at baseline, and then at month 1 (day 30 post-transplant) and month 2 (day 60 post-transplant). No further monitoring is required beyond this time, as pacritinib will be tapered off within the subsequent month on this trial. In the event of grade 1 or greater QTcF prolongation, EKG must be checked within 7 days of holding treatment to determine if treatment may be resumed by the above rules.

All patients will have a pre-transplant ECHO or MUGA performed to evaluate left ventricular ejection fraction. Patients will be monitored closely as standard care for allogeneic HCT (daily until engraftment and then at least once a week if not more until day +100). A full cardiopulmonary exam will be performed at each scheduled visit to clinically monitor for any signs or symptoms of heart failure as recommended by the National Institute for Health and Care Excellence (NICE)⁴⁰. Repeat ECHO will be performed at the 1 month and 3 month mark from initiation of pacritinib therapy (i.e. +30 and +90 days

from day 0) in keeping with monitoring recommended in the pacritinib Investigator Brochure. Dose management for left ventricular dysfunction is as follows:

LV dysfunction: CTCAEv4 Toxicity Grade*	Management/Action
G1	No change
G2 (first occurrence)	Hold treatment
*LVEF < 40%	Repeat echocardiogram 14 days.
	If the treatment resolved to ≤ grade 1,
	treatment may be resumed at next lowest
	dose level.
G2 (second occurrence)	Discontinue treatment
G3 and G4**	Discontinue treatment

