^{*}The CTCAE v4 term 'left ventricular systolic dysfunction' and its grading are based on the degree of clinical manifestations and therapy needed to control this issue. In contrast, specific cut-off values for abnormal ejection fraction are not provided, and grades 1 and 2 AE have no other descriptors. Detail is only provided for grade 3 ("symptomatic due to drop in ejection fraction responsive to intervention"). To be included on this trial, patients must have at least an ejection fraction of 45%. Adhering to accepted definitions of LV systolic dysfunction, we will consider a decline in LV ejection fraction to less than 40% as an event worthy of holding pacritinib therapy (and treat this as the equivalent of grade 2 per above). To resume therapy, a repeat echocardiogram within 14 days of stopping pacritinib must show return to > 45% ejection fraction.

After dose reduction, no dose re-escalation is allowed.

Management of Gastrointestinal Toxicity

The need for managing GI effects of pacritinib, particularly diarrhea, should be anticipated. A careful baseline evaluation of bowel habits (frequency and consistency of bowel movements) should be obtained at baseline for all patients.

Dose reduction rules for pacritinib (combined with SIR/TAC)		
Diarrhea	Current Dose (pacritinib)	Dose Reduction (pacritinib)
None / responds to antimotility agents	200mg twice a day	N/A
≥1500ml/day x3 days*	200mg twice a day	200mg qAM and 100mg qPM
	200mg qAM and 100mg qPM	200mg daily
	100mg twice a day	Hold pacritinib until stools are formed or volume is <500ml/day, then resume at 100mg twice a day and continue until day +70 taper. If diarrhea (≥1500ml/day x3 days) returns after holding pacritinib and does not respond to antimotility agents, patient comes "off-drug" but remains "on-study" for data collection and research labs.
	100mg daily	Hold pacritinib until stools are formed or volume is <500ml/day for at least 5 days, then resume at

^{**}As per above, symptomatic heart failure (grades 3 and 4 per CTCAE ver4) require complete discontinuation of pacritinib.

	100mg a day and continue until day +70 taper. If diarrhea (≥1500ml/day x3 days) returns after holding pacritinib and does not respond to antimotility agents, patient comes "off-drug" but remains "on-study" for data collection and research labs.
mote diarriea must be non-ini	ectious and unresponsive to anti-motility agents

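### Intracranial hemorrhage is dose-limiting at any grade but has no pacritinib dose rule of its own, and the general rule that covers it is laxer than the cardiac rules

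*Combined protocol and SAP*

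**What the plan says.** Item 7 of the DLT definitions (after Table 1) reads "Intracranial hemorrhage grade 1 or above". It carries no attribution condition and is the only listed DLT that starts below grade 3. Section V.5.e states: "Serious bleeding events, specifically bleeding of the brain (intracranial hemorrhage, subdural hematoma, cerebral hemorrhage), have been observed in association with pacritinib treatment". It adds that some of these outcomes were life-threatening or fatal.

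On dosing, Section VI.3 (Dose Adjustments for Pacritinib) says: "Specific dose adjustment rules are provided here for diarrhea, QTc prolongation, and left ventricular dysfunction". Everything else falls under a general rule that opens "For all other pacritinib-related (probably or definitely" and is limited to non-hematologic toxicity of grade 3 or higher. That rule holds the drug until grade 2 or better. It continues: "Once toxicity has returned to grade 2 or better, patients can resume pacritinib at 100mg less per" day than the dose at which the drug was held. It allows at most two such reductions, no dose under 100 mg daily, and no restart if recovery takes more than 14 days.

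The cardiac rules in the same section differ. For a first grade 2 QTcF event, the condition for resuming is that "toxicity resolves to ≤ grade 1 within 7 days"; grades 3 and 4 mean discontinuation. The LV table likewise requires grade 1 or better to resume after a held grade 2 event and discontinuation at grades 3-4, and a footnote repeats that "symptomatic heart failure (grades 3 and 4 per CTCAE ver4) require complete discontinuation of pacritinib".

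**The concern.** The protocol names two groups of serious, sometimes fatal pacritinib risk: cardiac events and brain bleeding. It gives the first group dedicated dose tables and leaves the second to a default clause written for unspecified toxicity. That clause is triggered by grade and by a fairly high level of attribution, and it permits restart at grade 2. An investigator following the text could therefore continue pacritinib through a low-grade brain bleed, or restart it while a severe one is only partly resolved, and be fully compliant. At stake is the safety of the individual patient with a bleed. DLT counting, the recommended phase II dose and the planned analyses are not affected.

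**Working it through.** The plan states no figure to reproduce. The check is a rule lookup followed by simple dose arithmetic.

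**Step 1. Which rule applies.** Intracranial hemorrhage is not among the three toxicities with specific rules, so the general rule in Section VI.3 applies, provided a brain bleed is read as non-hematologic. The protocol does not say. If it were read as hematologic, no dose rule would apply at any grade.

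**Step 2. What is required, by non-fatal grade.**

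| Event | Counts as a DLT? | Required pacritinib action |
|---|---|---|
| Bleed, grade 1-2, any attribution | Yes | None |
| Bleed, grade 3-4, possibly related or unrelated | Yes | None |
| Bleed, grade 3-4, probably or definitely related | Yes | Hold; may restart at grade 2 or better within 14 days, at 100 mg/day less |
| QTcF or LV dysfunction, first grade 2 event | Not decided by the dose tables | Hold; restart only at grade 1 or better, at the next lower dose level |
| QTcF or LV dysfunction, grade 3-4 | Not decided by the dose tables | Permanent discontinuation |

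**Step 3. Restart dose for a related grade 3-4 bleed.** Restart dose = current daily dose − 100 mg, with a floor of 100 mg daily.

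- Level 3, 200 mg twice daily: 400 − 100 = 300 mg/day (300/400 = 75%).
- Level 2, 100 mg twice daily: 200 − 100 = 100 mg/day (100/200 = 50%).
- Level 1, 100 mg daily: 100 − 100 = 0, below the floor, so the drug stops.

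Two other provisions lower the starting dose.

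- *CYP3A inhibitors (Section V.4.e).* Level 3 becomes 200 mg/day, so the restart dose is 100. Level 2 becomes 100 mg/day and level 1 becomes 100 mg every other day; neither has a lower permitted dose.
- *Taper (Table 2).* A patient on 200 mg twice daily at day +69 takes 200 mg daily from day +70 (restart 100) and 100 mg daily from day +84 (stop). A patient on 200 mg daily at day +69 takes 100 mg daily from day +70 (stop).

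Restart is therefore available only to patients above 100 mg/day who have not already used both permitted reductions.

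**Step 4. Whether other text closes the gap.**

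- The instructions announced in Section V.5.e concern TT, PT and PTT values, not a bleed. Appendix D as available is a study calendar.
- The toxicity stopping rule in Section VI.2, "If four related grade 4-5 unexpected adverse events occur in the conduct of this trial", halts accrual for the trial. It does not direct one patient's dosing.
- The 3+3 rules use a DLT to govern cohort escalation. They do not say what the affected patient should take.

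**The case against.** **Clinical judgement.** The text does not forbid a hold, and its restart wording is permissive. Most transplant physicians would stop the drug after a brain bleed. That is true, and it limits the practical risk. It would equally make the QTcF and LV tables unnecessary, yet the protocol wrote them.

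**The DLT grade is not a restart threshold.** A reader might infer that restarting at grade 2 contradicts the DLT definition. The documents do not support that: the DLT list serves escalation and the MTD, and nowhere sets a restart grade for an individual patient. The objection stands. The relevant comparison is with the cardiac dose tables.

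**Selective comparison.** The diarrhea table allows resumption at the same dose after a hold, and other DLTs such as myocardial infarction and GI hemorrhage also lack a table. Both facts are correct. Diarrhea, however, is described as common, mostly grade 1-2 and responsive to treatment. The other DLTs in items 1-6 start at grade 3, so a restart at grade 2 falls below the level the protocol counts. Whether the cardiac tables apply regardless of attribution is arguable: they state no such condition, but the wording of the general rule could imply that those toxicities are drug-related too.

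**Existing safeguards.** Coagulation and recent-bleeding exclusions, frequent visits, continuous monitoring by the principal investigator and monthly review all reduce risk. None is a dose rule for a bleed.

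**Completeness.** The Investigator Brochure and program standards are not available, so the finding is that no rule appears in this protocol as shown.

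**Conclusion.** The gap is real and minor. For a grade 1-2 intracranial bleed, and for a grade 3-4 bleed judged no more than possibly related, the protocol requires no pacritinib action. For a probably or definitely related grade 3-4 bleed it allows restart at grade 2, at 75% of the full level 3 dose or 50% of the full level 2 dose. Its own cardiac rules would require a permanent stop at those grades.

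A reader might go further and conclude that the protocol never forces a permanent stop after a brain bleed. That is not so: at 100 mg/day or less a related grade 3-4 bleed already ends treatment, as does failure to recover within 14 days. Nor does the text compel a restart.

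The conclusion assumes that a brain bleed counts as non-hematologic; the alternative reading widens the gap. How many patients could be affected cannot be derived from the documents. Section V.6 records that accrual was complete at this amendment, and dosing is planned to end near day +100, so the value lies with any patient still on drug and with later protocols that reuse the wording.

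**What to change.** Add one row for intracranial hemorrhage to the specific dose rules in Section VI.3:

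- Any grade: hold pacritinib at once.
- Grade 3-4: discontinue permanently, whatever the attribution, in line with the QTcF and LV tables.
- Grade 1-2: discontinue permanently if at least possibly related. Otherwise restart only after the bleed has resolved and the investigator has documented it as unrelated.
- The general restart at grade 2 or better does not apply.

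The general rule and the three existing tables stay as they are. No new procedures are needed.

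The cost is that an occasional patient loses pacritinib prophylaxis. A phase I patient with a bleed remains evaluable through the DLT itself (Section V.7), but a stop before day +21 can remove an on-drug value from the cohort's average pSTAT3, which steers escalation. In phase II, a stop before day +21 can make the patient non-evaluable and require a replacement. After day +21, the Withdrawal rule excluding patients off drug for more than 4 weeks is written for consent withdrawals; if it were also applied to toxicity stops, such a patient could drop out of the GVHD analysis.

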Appendix A: Acute GVHD grading system

Recommended staging and grading of acute GVHD Table 1

	Extent of organ involvement				
	Skin	Liver	Gut ·		
Stage 1	Rash on <25% of skin ^a	Bilirubin 2–3 mg/dl ^b	Diarrhea >500 ml/dayo or persistent nausea		
2 3 4	Rash on 25–50% of skin Rash on >50% of skin Generalized erythroderma with bullous formation	Bilirubin 3–6 mg/dl Bilirubin 6–15 mg/dl Bilirubin >15 mg/dl	Diarrhea >1000 ml/day Diarrhea >1500 ml/day Severe abdominal pain with or without ileus		
Grade ^e I II III IV ^f	Stage 1-2 Stage 3 or - Stage 4 or	None Stage 1 or Stage 2–3 or Stage 4	None Stage 1 Stage 2-4		

^{*}Use 'Rule of Nines' or burn chart to determine extent of rash

Bone Marrow Transplant. 1995 Jun;15(6):825-8.

1994 Consensus Conference on Acute GVHD Grading.

Przepiorka D1, Weisdorf D, Martin P, Klingemann HG, Beatty P, Hows J, Thomas ED.

^{*}Range given as total bilirubin. Downgrade one stage if an additional cause of elevated bilirubin has been documented

Volume of diarrhea applies to adults. For pediatric patients, the volume of diarrhea should be based on body surface area. Gut staging criteria for pediatric patients was not discussed at the Consensus Conference. Downgrade one stage if an additional cause of diarrhea has been documented. Persistent nausea with histologic evidence of GVHD in the stomach or duodenum

^{*}Criteria for grading given as minimum degree of organ involvement required to confer that grade

^{&#}x27;Grade IV may also include lesser organ involvement but with extreme decrease in performance status

Appendix B: comorbid conditions

i. Comorbidity score per Sorror, et al.

Comorbidity	Definition of comorbidities included in the new HCT-CI	HCT-CI weighted scores		
Arrhythmia	Atrial fibrillation or flutter, sick sinus syndrome, or venricular arrhythmias	1		
Cardiac	Coronary artery disease, congestive heart failure, myocardial infarction, or EF <50%	1		
Inflammatory bowel diseases	Crohn disease or ulcerative colitis	1		
Diabetes	Requiring treatment with insulin or oral hypoglycemics but not diet alone	1		
Cerebrovascular disease	Transient ischemic attack or cerebrovascular accident	1		
Psychiatric disturbance	Depression or anxiety requiring psychiatric consult or treatment	1		
Hepatic, mild	Chronic hepatitis, bilirubin > ULN to 1.5 X ULN, or AST/ALT > ULN to 2.5 X ULN	1		
Obesity	Patients with a body mass index >35 kg/m2	1		
Infection	Requiring continuation of antimicrobial treatment after day 0	1		
Rheumatologic	SLE, RA, polymyositis, mixed CTD, or polymyalgia rheumatica	2		
Peptic ulcer	Requiring treatment	2		
Moderate/severe renal	Serum creatinine >2 mg/dL, on dialysis, or prior renal trnasplant	2		
Moderate pulmonary	Adjusted DLCO and/or FEV1 66%=80% or dyspnea on slight activity	2		
Prior solid tumor	Treated at any time point in the patient's past medical history, excluding nonmelanoma skin cancer	3		
Heart valve disease	Except mitral valve prolapse	3		
Severe pulmonary	Adjusted DLCO and/or FEV1 <65% or dyspnea at rest or requiring oxygen	3		
Moderate/severe hepatic	Liver cirrhosis, bilirubin > 1.5 X ULN, or AST/ALT > 2.5 X ULN	3		

^{*}composite score obtained by summing total points

Version 8.0 40

^{*}psychiatric disturbance: only those with psychiatric disturbance (such as depression and/or anxiety) requiring therapy or treatment will be assigned 1 point on this measure.

^{*}modification made to "pulmonary" co-morbidity: given marked discrepancy in frequency distribution of reduced DLCO in analysis of 59 contemporary patients from our center compared to published standards, decrement in DLCO alone will not factor into calculation of "pulmonary" comorbidity. Only those with DLCO < 50% will be considered to have "severe pulmonary" comorbidity and be excluded from the trial.

TABLE 4. EXPECTED TRANSPLANT/GVHD-RELATED TOXICITIES IN HSC TRANSPLANT PATIENTS.

Category	Symptoms/Event	Category	Symptom/Event			
Dermatological	Pruritus Rash/dermatitis associated with high-dose chemotherapy or GVHD	Renal/Genitourinary	Bladder spasms Creatinine elevation Dysuria frequency-urgency Urinary retention			
Constitutional	Fever, Rigors, Chills	Reproductive	Persistent amenorrhea			
Gastrointestinal	Gastritis Colitis Dehydration Diarrhea associated with GVHD Nausea/vomiting Dysphagia Stomatitis/pharyngitis Hematocheza/melena Abdominal pain or cramping	Metabolic/Laboratory	Acidosis/alkalosis Amylase/lipase elevation Hypo- /Hyperglycemia Hypo- /Hyperkalemia Hypo- /Hypermagnesemi a, Hypophosphatemi a Jypo- /Hypermatremia Hypertriglyceridemia Hyperuricemia			
Hepatic	Lft elevation Bilirubin elevation Hypoalbuminemia Hepatomegaly	BMTComplex/ Multicomponent Events	GVHD Stem-cell infusion complications Venoocclusive Disease			
Cardiovascular	Edema Hypertension/Hypotension Sinus tachycardia	Hematologic	Cytopenias Catheter associated venous thrombosis			
Infections	Bacterial, fungal and/or viral infections Sepsis					

BMT = Bone marrow transplant; LFT = Liver function test.

